### Cohort B:

The comparisons between devices (e.g. GENEActiv vs Panoramic Bracelet) will be investigated with mixed effect models. Necessary covariates will be included such as demographic variables such as age, gender, proximity of the device and floor type. Pairwise comparisons will also be performed with paired t-tests or their non-parametric equivalent (Wilcoxon Signed-rank test). Mean absolute percent error between the comparator and reference metrics will be computed and Bland-Altman plots and 95% limits of agreement will be used to assess the bias. The endpoints might be log transformed using  $\log(x+1)$ .

To assess the relationship of endpoints between devices, Deming regression will be used. Deming regression takes into account the variations from the multiple measures on both test devices and traditional methods. The slope and intercept from model fitting and their 95% CI

will be reported. The ratio of variances of the two devices will also be calculated. Weighted Deming and Passing-Bablok regression may also be used if deemed appropriate.

P-values will be generated where appropriate and any p-value < 0.05 will be considered statistically significant. If multiple p-values are generated, an experiment wise significance threshold might be provided for context using methods such as family wise error rate (FWER) and/or false discovery rate (FDR) control. P-values will be rounded to 3 decimal places and therefore presented as 0.xxx; P-values smaller than 0.001 will be reported as ‘<0.001’.

Agreement between two measurements will be assessed by the intra-class correlation coefficient (ICC, type 2 way random effects, absolute agreement), according to the same benchmarks used in Cohort A. The ICC will be computed and compared between each pair of endpoints, using mean/median/25% & 75% quantiles across daily records.

## 5.2. Methods to Manage Missing Data

All summaries and analyses will be based on observed data and missing data imputation is not planned.

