
To assess the ability of pediatric participants to perform a battery of lab-based tasks.	
Number of participants (overall and per age group) able to perform each of the 7 tasks and task-completion percentage (among total of 7 tasks) per participant.

To assess the compliance in wearing the ActiGraph devices at home.	
Number of hours per day wearing the device and number of days with more than 10 hours of wearing time for each participant.

To evaluate the participant's or caregiver's perception of wearability and comfort of ActiGraph and APDM devices during in-lab sessions.	
In-lab ActiGraph/APDM wearability/comfort questionnaire responses from Visit 1 (Day 1).

 To evaluate the participant's or caregiver's perception of wearability and comfort of ActiGraph devices during the at-home monitoring period. 	
 At-home ActiGraph wearability/comfort questionnaire responses from at-home monitoring period in the Final Study Evaluation (Day 15 + 3 days).

 To evaluate the effect of floor surface (carpet vs tile) on gait metrics collected using ActiGraph and APDM devices. 	
 Gait metrics defined in the Annex 2 (eg, gait speed, stride length) measured by ActiGraph and APDM devices across different floor surfaces.
Tertiary/Exploratory Objective(s):	Tertiary/Exploratory Endpoint(s):

 To investigate the feasibility of using a daily activity diary to provide context in pediatric physical activity data collected by ActiGraph devices at home in pediatric participants. 	
 Daily activity diary responses and metrics related to physical activity endpoints from ActiGraph (eg, sedentary time as defined in Annex 3).

 To compare gait speed collected using the SIMI system and GAITRite® walkway, during in-lab sessions. 	
 Gait speed defined in the Annex 2 measured by SIMI system and GAITRite® walkway.

COHORT B: Panoramic Bracelet Device

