Cohort B: The position of the GENEActiv device and the Panoramic Bracelet device [closeness to the wrist] will be balanced per age group. Approximately half the participants in each age group will wear the Panoramic Bracelet device proximal to the wrist and the GENEActiv device more distal to the wrist and vice versa.

Follow-up Phone Interview (Day 15+3 days)

The follow-up visit will be conducted as a phone interview at the end of the 2 week at-home monitoring period (Day 15+3 days to allow for flexibility in scheduling) to record any AEs, any issues with devices and to remind participants to send back the devices. The participant will also answer a [Wearability/comfort questionnaire \(Annex 5\)](#) (Cohort A only) during the follow-up phone interview. This phone interview will be scheduled during Visit 1. The study site staff should make at least 2 attempts to contact the participant's legal representative by phone. All attempts should be documented. The devices will be sent back to Pfizer in a prepaid envelope (envelope given to the participant during Visit 1).

Any event with the devices (both reference and under study), the impact of this event, and the action taken with device will be recorded in the device assessment CRF.

Lost-to-follow-up

Lost-to-follow-up is defined by the inability to reach the participant's parent(s)/LAR after a minimum of 2 documented attempts (eg phone calls, e-mails). All attempts should be documented.

If a participant is lost-to-follow-up, the investigators will attempt to contact the participant's parent(s)/LAR to ask that the participant return the devices. If the participant's parent(s)/LAR cannot be contacted or refuses to return the devices, a report will be filed in the trial master file (TMF)/Clinical Study Report (CSR) to account for the loss of the device.

ASSESSMENTS

Additional Research

Not applicable.

Assessment of Suicidal Ideation and Behavior

Not applicable.

Biological Samples

Not applicable.

Imaging Assessments

Not applicable.

Rater Qualifications

Not applicable.

Medical/Surgical History, Prior/Concomitant Treatments

The medical/surgical history, prior/concomitant treatments will be collected by a medically qualified individual and recorded in several CRFs.

Body Weight and Height

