The proposed sample size for this study is approximately 39 participants in each cohort (approximately 13 in each age group). To the best of our knowledge, no relevant data has been published before to validate accelerometry-measured gait metrics against GAITRite® walkway or APDM in pediatric population. Using data from X9001198 study (healthy adult participants, ages 18-40 and 65-85 years), the Intraclass Correlation Coefficient (ICC) between gait speed obtained from the sensor data vs gait speed obtained from the reference comparator gait mat was 0.72 (when corrected for a systematic bias of 0.17 m/s). The ICC value for the null hypothesis is derived by using the median value of the lower bound of ICC for all gait metrics (8 spatial and temporal metrics). ICC_{null} was 0.27, range = [0, 0.66]. In order to reach ICC value of 0.72 with ICC_{null} value of 0.27 using a one-tailed test with alpha = 0.05 and power = 0.8 it is estimated that at least 17 participants will be needed. Therefore, approximately 20 adult participants (anticipating 15% attrition) are required for the validation analyses. Here, we double the amount to roughly 40 participants to account for potential higher variance in the healthy pediatric participants (ages 3 – 17). Since we have 3 age groups, each group will equally have 13 participants, which results in a total of 39 participants.

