## 3.2. Secondary Endpoints

**Table 4. Secondary Objectives and Endpoints (Cohort A)**

Secondary Objective(s):	Secondary Endpoint(s):

 
• To assess the feasibility of recruiting pediatric participants to conduct a wearable device study.
 
	
 
• Recruitment data listed by age group:           
 
(a) Number of participants contacted
 
(b) Number of participants screened
 
(c) Number of participants enrolled over time
 
(d) Time taken (number of days) to enroll approximately 13 participants per group
 
 
 

 
• To assess the ability of pediatric participants to perform a battery of lab-based tasks.
 
	
 
• Total number of participants able to perform each of the 7 tasks
 
• Number of participants per age group able to perform each of the 7 tasks
 
• Percentage of tasks completed (from a total of 7 tasks)
 

 
• To assess the compliance in wearing the ActiGraph devices at home.
 
	
 
• Number of hours per day wearing the lumbar and wrist devices
 
• Number of days with more than 10 hours of wear time for lumbar device
 
• Number of days with more than 18 hours of wear time for wrist device
 

 
• To evaluate the participant's or caregiver's perception of wearability and comfort of ActiGraph and APDM devices during in-lab sessions.
 
	
 
• Wearability/Comfort Questionnaire for APDM device and for Actigraph lumbar and wrist device separately (All questions are on a 5-point Likert scale)
 
• Cognitive Debrief of Wearability/Comfort Questionnaire
 

 
To evaluate the participant's or caregiver's perception of wearability and comfort of ActiGraph devices during the at-home monitoring period.
 
	
 
Wearability/Comfort Questionnaire for Actigraph lumbar and wrist device separately (All questions are on a 5-point Likert scale)
 

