#### 6.4. Secondary Objectives (Cohort B)

##### 6.4.1. To assess the compliance in wearing the Panoramic Bracelet device at home.

Compliance information for at-home deployment (~Days 1-7) will be based on wear time parameters (Section 3.1.2.3) derived from the Panoramic Bracelet device. First and last day may be removed for this analysis as we do not expect whole 24 hours of data.

Summary statistics will be computed for the wear endpoints across all participants and by age group. Box and whiskers plots (in hours and percentage of the day) across participants will be provided.

Two definitions of compliant days will be derived: 1) >10 hours of wear time, and 2) >18 hours of wear time per day. The summary statistics will be presented in a table.

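### At-home hours per day are summarised from observed data only, so mean wear per enrolled child is likely overstated if the children and days without a record had less wear

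*SAP*

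**What the plan says.** **Missing data.** SAP 5.2 has one rule for everything: "All summaries and analyses will be based on observed data and missing data imputation is not planned". SAP 6.3.3 (Cohort A) and 6.4.1 (Cohort B) summarise wear over all participants and by age group. Neither states a denominator or says how to treat a child or a day without a record. The Full Analysis Set in SAP section 4 contains every enrolled child.

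**Loss of data.** The protocol, under Lost-to-follow-up, foresees a parent or representative who "cannot be contacted or refuses to return the devices"; the stated response is a report on file. Under Study Design, children who drop out for non-safety reasons may be replaced, and each age group recruits until it has 13 completers. Under Study Size, the gait calculation concludes that "approximately 20 adult participants (anticipating 15% attrition) are required for the validation analyses".

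**Days analysed.** SAP 6.3.3 removes the first and last day outright. SAP 6.4.1, which covers about Days 1-7, leaves this open: "First and last day may be removed for this analysis as we do not expect whole 24 hours of data". The protocol (Devices Assessment and Exposure) has the bracelet worn at home from Day 1 to Day 15+3 days.

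**Cut-offs.** The protocol's Cohort A endpoint is hours per day and "number of days with more than 10 hours of wearing time for each participant", with no distinction by body site. SAP Table 4 and 6.3.3 use >10 h for the lumbar device, but for the wrist "Number of days with more than 18 hours of wear time for wrist device". SAP 6.4.1 derives both cut-offs for Cohort B.

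**The concern.** For most endpoints here, analysing observed data is a reasonable choice. Compliance is different, because a day can be missing for the very reason that the endpoint is meant to capture: the child stopped taking part or the device never came back. Devices are mailed back and no upload from home is described, so an unreturned device probably means no wear record at all. Replacing drop-outs and recruiting to a completer target add further finishers to the observed set.

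The protocol's rationale says that the compliance results are meant to reduce risk in later paediatric protocols. A planner needs the wear to expect per child enrolled. A figure based only on children with records answers a narrower question, and nothing in 6.3.3 or 6.4.1 would show how far the two differ.

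The day rule and the wrist cut-off affect the same tables. They raise separate matters: an unneeded open choice, and a protocol endpoint that goes unreported.

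**Working it through.** **1. The plan's own figure.** No compliance rate or target is stated. The nearest stated figure that carries a loss rate is the gait sample size, which takes an "ICC value of 0.72 with ICC_{null} value of 0.27" and, at one-sided alpha 0.05 and 80% power, arrives at a minimum of 17 children or adults analysed. I used the Walter, Eliasziw and Donner approximation with k = 2 measurements:

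- θ = ICC/(1 − ICC); C = (1 + kθ₀)/(1 + kθ₁); n = 1 + 2k(z_α + z_β)² / [(k − 1)(ln C)²].
- Gait, 0.72 against 0.27: n = 16.54, so 17; 17/0.85 = 20. Reproduced.
- Cohort B sleep, 0.88 against 0.36: n = 7.20, so 8; 8/0.85 = 9.4, so 10 per age group. Reproduced.

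The 15% is thus an allowance for sample size. It is not a forecast of device return.

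**2. Children with no at-home record.** Let d be the share without a record and M the observed mean. If their true wear is zero, the mean over all enrolled is M × (1 − d).

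| Observed M (h/day) | d | Over all enrolled (h/day) |
|---|---|---|
| 20 | 5% | 20 × 0.95 = 19.0 |
| 20 | 10% | 20 × 0.90 = 18.0 |
| 20 | 15% | 20 × 0.85 = 17.0 |
| 20 | 20% | 20 × 0.80 = 16.0 |
| 18 | 15% | 18 × 0.85 = 15.3 |
| 22 | 15% | 22 × 0.85 = 18.7 |

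The values of M are assumptions, because the documents give none. For a given d, zero wear makes each row an upper bound on the overstatement.

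In numbers of children, 39 completers at 15% loss means 39/0.85 = 45.9, so about 46 enrolled per cohort. About 46 − 39 = 7 would then add nothing to the summary if none left a record.

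**3. A child with partial data.** Assume a Cohort A child wears the wrist device 20 h on Days 2, 3 and 4 and withdraws on Day 5, with nothing recorded afterwards. Day 1 and the child's own last day are removed.

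- Observed mean: 60/3 = 20 h/day.
- Over the 13 planned days (Days 2-14): 60/13 = 4.6 h/day.
- Days >18 h: 3.

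The hours-per-day mean hides the early exit. The compliant-day count shows it.

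**4. Day rule, Cohort B.** Days 1-7 without Day 1 leave six days. Dropping Day 7 as well leaves five of six. The stated reason is an incomplete 24 hours, but the bracelet stays on to Day 15, so Day 7 is a full wear day. Nothing in the documents shows whether dropping it raises or lowers mean wear.

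**5. Wrist cut-off, Cohort A.** With daily wear assumed normal (illustration only):

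| Mean / SD (h) | Days >10 h | Days >18 h |
|---|---|---|
| 20 / 3 | 99.96% | 74.8% |
| 18 / 4 | 97.7% | 50.0% |
| 16 / 4 | 93.3% | 30.9% |

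The SAP's cut-off is the stricter one, so it lowers reported compliance.

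**The case against.** The strongest case on the other side has five parts.

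- **Stopped wear is mostly observed.** A returned device that recorded while off the wrist contributes low hours under SAP 5.2. This stands: only unrecorded days are lost.
- **The shortfall is partly visible.** Section 5.1 reports n with the summaries, device events go on a CRF, and Cohort B reports available hours beside wear hours. This stands in part. The n shows that children are missing but not why, and available hours describe only devices that left a file.
- **Scoring missing days as zero has its own bias.** A device worn daily and then lost would score zero, and withdrawal can be for safety or administrative reasons. This stands, and is why the zero-wear figure belongs in a sensitivity summary and not in the headline.
- **The wrist cut-off is reasonable.** The wrist device is to be worn continuously, and 18/24 is 75% of the day against 42% for 10 h. The SAP may also modify a secondary endpoint without a protocol amendment. Both stand. The protocol's endpoint still goes untabulated for the wrist.
- **Day 7 may be a transition day.** GENEActiv is added at about that time (Day 7+2) and the window is approximate. But adding a second device does not shorten the bracelet's own recording, which is the reason the SAP gives.

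A reader might also infer that the day and cut-off rules inflate compliance, or that the cohorts cannot be compared. The documents support neither: the direction of the day rule is unknown, >18 h is stricter, and wrist days >18 h are derived in both cohorts.

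**Conclusion.** The point holds conditionally. Under SAP 5.2, the hours-per-day summaries in 6.3.3 and 6.4.1 describe recorded days, not enrolled children over scheduled days. Mean wear per enrolled child is likely overstated if the children without records wore the device less. With 20 h/day observed, the overstatement is at most 3 h/day (20 − 17) if 15% have no data, and at most 1 h/day (20 − 19) if 5% do. These bounds assume zero true wear in the children without data and use an attrition allowance as a stand-in for the share without data.

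A reader might infer that compliance is certainly overstated, or that 17 h/day is the expected value. The documents do not support that, because they give neither a no-data rate nor any information on wear among the missing. Nor does the loss carry over fully to the compliant-day count: only a child with no record at all disappears from it.

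Two separate points remain, and neither is shown to bias compliance upward. The reason given for dropping the last day does not fit Day 7 in Cohort B, and the protocol's >10 h endpoint is not reported for the Cohort A wrist device. All of this should be settled in the SAP before analysis, because compliance figures for later trials are one of the study's stated outputs.

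**What to change.** - **6.3.3 and 6.4.1:** keep the observed-data summary. Beside it, as a sensitivity summary, show one over all enrolled children and all scheduled days, with unrecorded days from withdrawal, loss or non-return counted as non-wear. Keep documented device faults separate.
- **Same tables:** give the number of children and of days without data, by reason.
- **6.4.1:** replace the optional removal of first and last day with removal of Day 1 only.
- **6.3.3 and Table 4:** add wrist days >10 h beside wrist days >18 h.

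The cost is SAP wording and one or two extra table columns. No new data are needed for the >10 h count, which comes from the same wear variable. The sponsor would also have to report a lower-bound compliance figure that looks less favourable than the observed one.

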## 6. ANALYSES AND SUMMARIES

### 6.1. Primary Objective (Cohort A): To compare gait quality metrics collected using ActiGraph devices, APDM devices and GAITRite® walkway, during in-lab sessions.

The list of common device data and comparisons are listed in Table 8. We will compare the common endpoints derived from Actigraph worn on the lumbar position (test device) with respect to GAITRite and APDM.

**Table 8. Specific Endpoints and Analyses for Primary Objective (Cohort A)**

Task	Devices	Measurements/comparisons
In-lab walk at natural speed	Reference: GAITRite, APDM (Mobility Lab) Comparator: Actigraph Lumbar (gaitPy)	Common gait metrics* (Comparison across devices)
In-lab walk at slow and fast speed (self-paced)	Reference: GAITRite, APDM (Mobility Lab), Comparator: Actigraph Lumbar (gaitPy)	Common gait metrics* (Comparison across devices)
In-lab Simulated Activities	Reference: APDM (free living method) Comparator: Actigraph Lumbar (gaitPy)	Common gait metrics* (Comparison across devices)
In-lab Simulated Activities	Reference: APDM (free living method) Comparator: Actigraph Wrist, Actigraph Lumbar (gaitPy)	Number of Steps (Comparison across devices)

\* Common gait metrics between devices are Double Support Time, Single Limb Support Time, Stance Time, Swing Time, Step Duration, Stride Duration, Stride Length, Gait Speed, and Cadence, as in Section 3.1.1.1 and 3.1.1.2.

Appropriate summaries and plots for each digital endpoint will be produced **per task** (colored by age group, if necessary) as follows:

- Scatter plots of digital metrics from each reference device vs comparator device with corresponding regression line and 95% confidence interval (CI) will be plotted.
- Accuracy of the sensor-derived metrics will be determined by computing the mean difference, mean absolute difference, variation of the difference, the mean percent error, the mean absolute percent error and the effect size between reference device(s) and comparator device metrics.
- Bias will be assessed by Bland-Altman plots and 95% limits of agreement between each reference devices and comparator device. Specifically, the following error measures will be computed: mean difference, lower and upper 95% limit of agreement.
- Intra-class correlation coefficient (ICC) and its lower and upper confidence limits between metrics derived from reference devices and comparator device will be computed.
- For in-lab walk at natural, slow and fast speed tasks, the ICC will be used to compare gait endpoints derived from APDM, GAITRite and Actigraph lumbar sensor.
- The correlation coefficients (Pearson's) between metrics from each reference device and comparator device will be calculated.
- Box and whisker plots of digital metrics from each reference device and comparator device will be plotted.
- Mixed model regression analyses will be used to investigate the effect of device (e.g., GAITRite, APDM, Actigraph), and the interaction between device and task (normal/slow/fast speed walks) on each gait metric. The device, task, and their interaction will be fixed effects, and subject will be entered as random effect. Post-hoc t-tests might be performed between devices. Multiple comparisons, when necessary, will be performed using FDR. Age (or age group) and sex may be used as covariates in the models. The estimates for fixed effect parameters, standard errors, 95% CIs, and p-values, as well as the variance estimates for the random effect will be summarized. Results from all models will be presented in a table. Furthermore, Least Squares Means (LSMeans) together with their 95% CI will be calculated for each of the device-task combination (e.g. LSMean of GAITRite gait speed for normal walk task).

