5. Participants who self-report any medical condition (including pregnancy) and/or medication use, or in the investigator's opinion, any medical or psychiatric condition, and/or use of medications such as but not limited to antipsychotics, hallucinogens, amphetamines, barbiturates, etc, that may affect the safety of the participant and may interfere with the conduct of the study.
6. Other medical or psychiatric condition that may increase the risk of study participation or, in the investigator's judgment, make the participant inappropriate for the study.
7. Participants with known allergies to components as specified by device manufacturer if applicable (eg, plastic, stainless steel and silicone).

Variables

The study will enroll pediatric qualified participants at a single center in Cambridge, MA. Potential confounding variables including age, gender and race will be assessed at the start of

study procedures and be adjusted for as necessary in the statistical analysis, as noted in the Statistical Analysis Plan (SAP) and **DATA ANALYSIS** Section.

The following variables will be measured for each age group:

- Gait metrics defined in [Annex 2](#) (eg, gait speed, stride length) measured by APDM devices and GAITRite® walkway, device under study, SIMI system and GENEActiv (for Cohort B only)
- Measures of the recruitment: number of participants contacted, screened and enrolled over time, time to enroll approximately 13 participants per group, mean number of participants recruited per month (overall and per group).
- Measures of the ability to perform a battery of lab-based tasks: number of participants (overall and per age group) able to perform each of the 8 tasks and task-completion percentage (among total of 8 tasks) per participant.
- Measures of the compliance in wearing device under study at-home: number of hours per day wearing the device and number of days (>10 hours per day) wearing the device for each participant.
- Measures of the perception of wearability/comfort of the device under study and APDM (Cohort A only) devices: wearability/comfort questionnaires answers.
- Daily activity diary answers. (Only Cohort A)
- Daily activity and sleep diary answers Only Cohort B)
- Physical activity endpoints from devices under study (eg, sedentary time, sleep as defined in [Annex 3](#))

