The proposed sample size is appropriate for assessing the association of other metrics, such as sleep, across devices in Cohort B. Using data from previous study (NCT03898427, healthy participants 18 years and older), data from 21 participants wearing ActiGraph and GENEActiv on their wrists simultaneously. The ICC value of total sleep time obtained from ActiGraph and GENEActiv devices averaged across both arms at Visit 1 was 0.88. The ICC value for null hypothesis was computed by randomly breaking the participant pairings 1000 times and computing the 95th percentile of the ICC values of these randomly assigned pairs (ICC_{null} was 0.36). In order to reach ICC value of 0.88 with ICC_{null} value of 0.36 using a one-tailed test with alpha = 0.05 and power = 0.8 it is estimated that at least 8 participants (10 participants to be recruited, anticipating 15% attrition, per age group, total 30 participants) will be needed. Therefore, we will have appropriate power (more than 95%) to be able to assess metrics per age group such as total sleep time between devices in Cohort B. In Cohort B, considering higher variability in pediatric population and to be able to provide consistent gait comparison analysis across cohorts, we will recruit the same number of participants as in Cohort A.

It is anticipated that the proposed sample size will achieve the following goals: (1) assess the agreement of gait metrics from ActiGraph and Panoramic Bracelet against reference comparators; (2) provide data on usability, wearability and comfort of ActiGraph and Panoramic Bracelet for future clinical trials, and (3) assess the agreement of other metrics such as related to sleep and scratch from Panoramic Bracelet against comparators. The data obtained in this study will enable power calculations for future pediatric studies.

Data Management

Gait metrics (eg, gait speed, stride length, etc.) will be extracted from GAITRite® walkway, APDM, and the devices under study (using GaitPy algorithm). Physical activity metrics will be extracted from the device under study (using devices provided software), for Cohort B GENEActiv data will be included.

In addition, participant's medical history, medication history and demographics, height, and weight will be collected as potential confounding variables.

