### Cohort A:

The comparisons between devices (e.g. APDM vs Actigraph) will be investigated with Mixed Model Repeated Measures (MMRM), ANOVA or a non-parametric equivalent (Kruskal-Wallis, Friedman tests). Necessary covariates will be included such as demographic variables such as age and gender, and floor type. Pairwise comparisons will be performed with paired t-tests or their non-parametric equivalent (Wilcoxon Signed-rank test). If visual inspection of the data suggests that a transformation of the endpoints should be performed, this will be applied as appropriate prior to analysis and documented in the final report as required.

P-values will be generated where appropriate and any p-value  $< 0.05$  will be considered statistically significant. If multiple p-values are generated, an experiment wise significance threshold will also be provided for context using methods such as family wise error rate (FWER) and/or false discovery rate (FDR) control. P-values will be rounded to 3 decimal places and therefore presented as 0.xxx; P-values smaller than 0.001 will be reported as '<0.001'.

Agreement between two measurements will be assessed by the intra-class correlation coefficient (ICC, type 2 way random effects, absolute agreement), according to the following benchmarks:  $ICC \leq 0.4$  indicates 'poor', 0.4 to 0.59 'moderate', 0.6 to 0.74 'good', and 0.75 to 1 'excellent' agreement. In addition, Bland–Altman plots and 95% limits of agreement (average difference  $\pm$  1.96 standard deviation of the difference) will be used to visualize and quantify differences between endpoints derived from the reference devices and comparator device (Actigraph).

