- For each day, accuracy of the sensor-derived metrics will be determined by computing the mean difference, mean absolute difference, variation of the difference, the mean percent error, the mean absolute percent error and the effect size between the Panoramic Bracelet device and GENEActiv (reference) device metrics.
- Box and whisker plots of digital metrics from the Panoramic Bracelet device and GENEActiv device will be plotted for each day.
- Bias, including the mean bias across days and bias from repeated measures, will be assessed by Bland-Altman plots and 95% limits of agreement between the Panoramic Bracelet device and GENEActiv device. Specifically, the following error measures will be computed: mean difference, lower and upper 95% limit of agreement. For assessing bias from repeated measures, both mean difference and 95% limits will be computed from the mixed effects model described above.
- Intra-class correlation coefficient (ICC) and its lower and upper confidence limits between metrics derived from the Panoramic Bracelet device and GENEActiv device will be computed, for mean/median/25% quantile/75% quantile across daily measures.
- Scatter plots of digital metrics from the Panoramic Bracelet device vs GENEActiv device with corresponding regression line and 95% CI will be plotted. The regression line and the 95% CI will be derived from the previous mixed effects model.

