##### 6.4.2. To compare gait quality metrics collected using Panoramic Bracelet devices, APDM devices and GAITRite® walkway, during in-lab sessions.

The common endpoints are derived from the Panoramic Bracelet device with respect to GAITRite and APDM. Same analyses plan will be implemented as listed in Section 6.1 Primary Objective (Cohort A).

Additionally, Deming regression will be used to assess relationship of endpoints between the comparator and reference devices while taking into account of variations from the multiple measures. The fitted slope, intercept and their corresponding 95% CI will be reported. Weighted Deming and Passing-Bablok regression may also be considered if deemed appropriate.

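### Cohort B is sized to assess agreement per age group, but no per-age-group ICC is listed; pooled gait ICCs need an age-adjusted companion

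*SAP*

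**What the plan says.** **Cohort B sizing.** Protocol, Study Size, takes an ICC of 0.88 against a null of 0.36 for total sleep time. It arrives at 8 evaluable participants, or 10 recruited, in each age group (30 in all), and concludes that "we will have appropriate power (more than 95%) to be able to assess metrics per age group such as total sleep time".

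**Cohort B analysis.** SAP 6.2.1 plans the "Intra-class correlation coefficient (ICC) and its lower and upper confidence limits between metrics derived from the Panoramic Bracelet device and GENEActiv device", for the mean, median and two quartiles across days. No age stratum is given. The protocol's Statistical Analysis section for the same objective also lists one ICC without an age split.

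**Gait.** SAP 6.1 says, per task, "Intra-class correlation coefficient (ICC) and its lower and upper confidence limits between metrics derived from reference devices and comparator device will be computed". SAP 6.4.2 adopts the same plan for Cohort B.

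**ICC type and labels.** SAP 5.1 defines a two-way random-effects, absolute-agreement ICC and grades it on fixed cut-offs (good from 0.6, excellent from 0.75).

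**Where age does appear.** SAP 5.1 says of the Cohort A device-comparison models: "Necessary covariates will be included such as demographic variables such as age and gender, and floor type". SAP 3.5 and the mixed models in 6.1 and 6.2.1 allow age as an optional covariate, and displays may be coloured by age group. For Cohort B wear-time compliance, 6.4.1 is explicit: "Summary statistics will be computed for the wear endpoints across all participants and by age group". None of this wording reaches the ICC.

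**The concern.** Two points follow, of unequal weight.

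The main one is a gap between sizing and analysis. The protocol justifies Cohort B by power to assess agreement within an age group. If the SAP is followed exactly, no within-group ICC is produced.

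The second is interpretive. An ICC is the share of total variance that lies between subjects. Pooling children aged 3 to 17 adds differences between age groups to that share without making either device more accurate. A pooled gait ICC can therefore look better than the agreement within a narrower age band. This matters because the protocol states a later use: "The data obtained in this study will enable power calculations for future pediatric studies". A study in one age band planned on the pooled value alone could be too small.

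**Working it through.** **1. Reproduce the plan's figures.** Inputs from Protocol, Study Size: two devices, one-sided alpha 0.05, power 0.80. With k = 2, write C = [(1+r0)/(1−r0)] / [(1+r1)/(1−r1)]. The usual ICC sample-size approximation is n = 1 + 4(1.645+0.842)² / (ln C)².

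- Sleep, 0.88 against 0.36: C = 2.125/15.667 = 0.136, ln C = −1.998, n = 7.2, so 8. With 15% attrition, 8/0.85 = 9.4, so 10. Both match.
- Gait, 0.72 against 0.27: C = 1.740/6.143 = 0.283, ln C = −1.262, n = 16.5, so 17. With attrition, 17/0.85 = 20. Both match.

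**2. Power in one age group.** Power = Φ(√((n−1)/4)·|ln C| − 1.645).

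- Sleep, n = 13: √3 × 1.998 − 1.645 = 1.815, power 96.5% (95.3% to 96.0% by exact F test). At n = 10 it is 89% to 91%. The claim of more than 95% is therefore correct for one group of 13.
- Gait, n = 13: √3 × 1.262 − 1.645 = 0.540, power 70.5%. At the pooled n = 39 it is 98.8%. Gait was sized on the pooled sample.

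**3. Effect of age spread on a pooled ICC.** The documents give no between-age variance, so a range is assumed. Let r be the within-age ICC without bias, d the gap between adjacent age-group means and b the device bias (d and b in within-group SDs). Three equal groups give a between-age variance f = 2d²/3, and

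pooled ICC = (r + f) / (1 + f + b²/2).

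With r = 0.50 (assumed):

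| d | 0 | 0.5 | 1 | 2 |
|---|---|---|---|---|
| b = 0 | 0.50 | 0.57 | 0.70 | 0.86 |
| b = 0.5 | 0.44 | 0.52 | 0.65 | 0.84 |

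For example, d = 1 and b = 0 gives (0.50 + 0.667)/(1 + 0.667) = 0.70.

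In simulated trials of 3 × 13 children (20,000 per cell, r = 0.50, b = 0), the pooled ICC earned the label good or better in 19%, 40%, 88% and 100% of trials at these four gaps. An ICC adjusted for age group stayed near 19% at every gap.

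**4. The opposite direction.** Take d = 0.5 and a device bias of +1, 0 and −1 SD in the three groups. The group ICCs are 0.33, 0.50 and 0.33. The between-group covariance of the two devices is −1/6 and each device's between-group variance is 1/6, so the pooled ICC is (0.50 − 0.167)/(1 + 0.167) = 0.29. Pooling need not inflate.

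**5. Later use, illustration only.** Against a null of 0.27, a true within-band ICC of 0.50 needs 85 participants. Planning on a pooled 0.57 or 0.70 gives 46 or 19, with true power of 57% or 31%.

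**6. Precision at n = 13.** 95% limits from the F distribution (12 and 12 df) are 0.65 to 0.96 at ICC 0.88, 0.30 to 0.91 at 0.72, and −0.04 to 0.82 at 0.50.

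**The case against.** The strongest reply is that the SAP departs from nothing. The per-group sentence sits in a sample-size justification; the protocol's Statistical Analysis section calls its list examples and has no per-group ICC, and SAP 6.2.1 matches that list. This stands. A reader might infer that the SAP dropped a prespecified analysis, and the documents do not support that. What remains is a stated purpose of the sizing that no listed analysis serves.

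For gait, a reader might infer a broken commitment from the protocol's Variables section ("The following variables will be measured for each age group"). That sentence describes what is measured and promises no ICC per group. The pooled ICC is also a legitimate estimate for the population studied, ages 3 to 17. Both replies stand.

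A reader might also infer that age is ignored, or that the pooled ICC is certainly inflated. Neither holds. The optional age terms and colouring can show age-related bias, and the difference model in 6.2.1 may carry age group as a fixed effect. These give no age-specific or age-adjusted ICC, however. Inflation is plausible for gait and uncertain for sleep, scratch and wear time, and step 4 shows that the direction can reverse.

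Finally, every inflation figure rests on assumed values of d and r. That is correct, and the size should be read as a range.

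**Conclusion.** The main point holds on the text alone. Cohort B's sizing claims per-age-group power, the claim is numerically right at 13 per group, and neither document lists the ICC that would use it.

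The gait point holds as a limit on interpretation. A pooled ICC can overstate agreement within a narrower age band, by an amount the documents do not allow one to fix. Under an assumed within-age ICC of 0.50, no bias and similar device error at all ages, the excess runs from 0.07 (0.57 − 0.50) to 0.36 (0.86 − 0.50) for gaps of 0.5 to 2 SD.

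The consequence is confined to correlation-type measures: the ICC, its label and Pearson's r. Bland-Altman limits and error measures do not benefit from age spread, and no success criterion depends on the label. The stated sample sizes and power need no correction. This is a worthwhile, inexpensive improvement; it does not invalidate the planned analysis.

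**What to change.** **SAP 6.2.1.** Beside the pooled ICC, report the ICC with 95% CI and the limits of agreement by age group, for the across-day mean of each endpoint only. With 11 endpoints and 3 groups that is 33 added ICCs; stratifying all four daily summaries would add 132.

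**SAP 6.1 and 6.4.2.** Report one age-adjusted ICC per gait metric and task as a supplementary estimate, with age group fixed and subject and device random. Mark it as an added analysis for Cohort A, whose data collection was planned to end on 01 April 2022, before the current SAP version of 01 Sep 2023.

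**Wording.** State that the pooled ICC and its 5.1 label apply to the full 3 to 17 range and should not be used alone to plan a study in one age band.

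**Cost.** SAP text, a few more tables and repeat runs on data already in the plan. Age adjustment costs almost no precision: at ICC 0.50 with 39 children the 95% CI is 0.22 to 0.71, against 0.22 to 0.70 unadjusted. Per-group intervals at n = 13 are wide, and each limit of agreement carries a 95% CI of ±1.06 SD of the differences, against ±0.56 at n = 39. Any per-group gait ICC would be descriptive only. Adjusting for age group still leaves some age spread within the 6 to 11 and 12 to 17 bands.
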